7.4.2 Modification of Study Therapy

Summary:

The following will be provided by treatment for each study drug.

- Number (%) of subjects with dose delay, omission and discontinuation with reason
- Infusion interruptions
 - Number (%) of subjects with at least one infusion interruption along with the reason
 - Number of infusion interruptions per subject
 - Number (%) of subjects with at least one IV infusion rate reduction along with the reason

Listing: All relevant information on dose modification listed above

7.4.3 Prior and Concomitant Medications

Prior and concomitant medications will be coded using the WHO Drug Dictionary. Concomitant medications are defined as medications other than study medications which are taken at any time on-treatment.

Summary:

The number (%) of treated subjects for the following will be provided by treatment:

- Summary table of prior therapy by tumor type and treatment group: include the settings of prior systemic cancer therapy, best responses, and number of prior regimens (0, 1, 2, and >=3), prior ipilimumab therapy and prior nivolumab therapy;
- Summary of non-study medication including prior and concomitant medications
- Concomitant immune-modulating medications for management of AE by medication class and generic term if applicable

Listing:

• All prior and concomitant medications.

7.5 Efficacy

Efficacy analyses based on Response-evaluable Participants may be performed as supportive analyses. If majority of All Treated Participants is included in Response-evaluable Participants, limited efficacy analyses will be performed on Response-evaluable Participants (eg, ORR). For interim analyses when the minimum follow-up period is less than sufficient to warrant adequate interpretation of the result, efficacy analyses may be performed on Response-evaluable Participants.

Time to event distribution (e.g. progression free survival, overall survival, and duration of response) will be estimated using Kaplan-Meier (K-M) method. When appropriate, the median along with 95% CI will be provided using Brookmeyer and Crowley methodology²⁴ (using log-log transformation for constructing the confidence intervals). Rates at fixed timepoints (e.g. PFSR at 6 months or OS at 12 months) will be derived from the K-M estimate and corresponding confidence interval will be derived based on the Greenwood formula using log-log transformation²⁵. Confidence intervals for binomial proportions will be derived using the Clopper-Pearson method.

In general, efficacy summaries will be provided by tumor type and treatment group.

Summary:

- ORR and DCR with corresponding 2-sided 95% CI, together with breakdown of BOR
- Duration of response, OS, and PFS with median (95% CI) and range (min, max) by K-M method. The number of subjects still in response at the time of data lock will be indicated
- Time to response with median (95% CI) and range (min, max) by K-M method

Figure:

- Maximum reduction in baseline target lesions (aka waterfall plot)
- Kaplan-Meier (K-M) plot of duration of response for responders only
- Swimmer plot of time to response and duration of response, including time on therapy for responders only
- K-M plot of PFS
- K-M plot of OS

Listing:

The following will be listed by tumor type and treatment group.

- By patient listing of all tumor lesion measurements by visit
- By patient listing of tumor evaluation at each visit
- Subject level efficacy for all treated subjects: tumor best overall response (BOR), maximum reduction in tumor burden from baseline, time to response, duration of response, time to progression, and death indicator

7.6 Safety

Analysis of safety will be based on All Treated Subjects and presented by treatment ("as assigned") and overall (if appropriate).

Adverse events (AEs) will be coded and grouped into Preferred Terms (PT) by System Organ Class (SOC) according to the most current version of MedDRA and be graded using the NCI Common Terminology Criteria for Adverse Events (CTCAE) version 4. Drug-related AEs are those events with relationship to study drug "Related" as recorded on the CRF. If the relationship to study drug is missing, the AE will be considered as drug-related. All AEs will be summarized and listed by SOCs and PTs.

Listing of adverse events will include all enrolled subjects as SAEs and deaths are collected pretreatment. Summaries of adverse events will include (1) events occurring from the first dose date to 150 days (inclusive) after the last dose of study drug for subjects who are off study treatment and (2) all events occurring from first dose date for subjects who are still on study medication.

When reporting adverse events by CTC grade, summary tables will be provided based on the event with worst CTC grade (independent of relationship to study medication). Subjects will only be counted (1) once at the preferred term (PT) level, (2) once at the system organ class (SOC) level, and (3) once in the 'Total subject' row at their worst CTC grade, regardless of SOC or PT.

The analysis of laboratory results will be based on All Treated Subjects. Laboratory results will be categorized according to NCI CTCAE (version 4.0) grade. Baseline is defined as the last nonmissing measurement prior to the first dosing date and time. Summaries of laboratory results include baseline and (1) post-baseline results up to 150 days (inclusive) after the last dose of study drug for subjects who are off study treatment and (2) all available post-baseline results for subjects who are still on study medication.

Summary tables will be generated for Part 1 and 2 combined. Listings will include all available data from Parts 1, 2, 3, and 5.

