6.2 Treatment Regimens

The treatment group "as randomized/assigned" will be retrieved from the IRT system, if applicable. The treatment group "as treated" will be the same as the arm as randomized/assigned by IRT. However, if a participant received an incorrect treatment for the entire period of treatment, the participant's treatment group will be defined as the incorrect treatment the participant actually received.

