7.2.3 Relevant Protocol Deviations

Non-programmable relevant eligibility and on-treatment protocol deviations, as well as significant (both programmable and non-programmable) will be reported through ClinSIGHT listings. The following programmable deviations from inclusion and exclusion criteria will be considered as relevant protocol deviations and a listing will be provided. The following programmable deviations from inclusion and exclusion criteria will be considered as relevant (i.e., protocol deviations that could potentially affect the interpretability of the study results).

At Entrance:

Subjects without measurable disease at baseline

Subject who received study medication less than 28 days from the last dose of the prior therapy

Subjects that have received greater than 5 prior treatment regimens

At Entrance for Expansion Cohorts:

Subjects with deviations on baseline or prior therapy related inclusion/exclusion criteria such as:

- NSCLC subjects:
 - who have not received prior platinum chemotherapy
 - with ALK translocation that have not received an ALK inhibitor
 - with an activating EGFR mutation that have not received an EGFR inhibitor
- Melanoma subjects:
 - who have not received prior therapy with ipilimumab
 - with BRAF mutation (V600E or V600K) present who have not received a RAF or MEK inhibitor.
- Colorectal Cancer (CRC) subjects:
 - without Microsatellite instability stable (no alterations) or microsatellite instability low (only one alteration)
 - without DNA mismatch repair gene proficient on tumor immunohistochemistry (IHC)
- Head and Neck Squamous Cell Carcinoma (SCCHN) (oral cavity, pharynx, larynx) subjects:
 - without evidence of progression or recurrence within six months of last dose of platinum therapy
 - with radiation therapy not completed at least 4 weeks prior to study drug administration
- Hepatocellular carcinoma (HCC) subjects
 - without Child-Pugh score of B
 - with hepatitis B infection with hepatitis B DNA viral load greater than 100 IU/mL and not on antiviral therapy
 - with hepatitis B infection with coinfection with hepatitis C or hepatitis D

On-treatment:

- Subjects receiving anti-cancer therapy while on study therapy
- Subjects treated differently than as assigned (subjects who received the wrong treatment for the entire study period, excluding the never treated)
- Subjects receiving greater than 10mg/day of prednisone or equivalent at the time of study drug administration.

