7.4 Extent of Exposure

The extent of exposure will be characterized according to the number of participants exposed, the duration of exposure, and the dose to which they were exposed. Analyses in this section will be performed on the All Treated Participants "as treated".

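### SAP 7.6 groups safety by assigned treatment and SAP 7.4 groups exposure by received treatment, so in Parts 1 and 2 a subject on the wrong treatment throughout would sit in different columns of the two sets of tables

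*SAP*

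**What the plan says.** Four places in the SAP bear on this.

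- **Section 6.2 (Treatment Regimens)** defines both groupings. By default the as-treated group "will be the same as the arm as randomized/assigned by IRT". The exception applies "if a participant received an incorrect treatment for the entire period of treatment"; that participant's "treatment group will be defined as the incorrect treatment the participant actually received".
- **Section 7.2.3 (Relevant Protocol Deviations)** lists "Subjects treated differently than as assigned" among the on-treatment deviations and describes them as subjects on the wrong treatment for the entire study period. The SAP therefore foresees the case.
- **Section 7.4 (Extent of Exposure)** reads "Analyses in this section will be performed on the All Treated Participants", on the as-treated basis. This covers duration of therapy, dose intensity and dose modification.
- **Section 7.6 (Safety)** reads "Analysis of safety will be based on All Treated Subjects and presented by treatment", on the as-assigned basis. This covers adverse events, serious adverse events, deaths, events leading to discontinuation and laboratory results.

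Two further provisions set the scope. Safety summary tables are produced for Parts 1 and 2 combined (SAP 7.6). Results of Parts 3 and 5 are listed only (SAP 7.1). Protocol 8.4.3 asks for adverse events by treatment and does not say on which basis.

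**The concern.** Exposure and safety tables are read together: so many subjects received this dose for so long, and these events occurred. That reading needs the same subjects in the same column. With two bases it fails for any subject whose assigned and received groups differ.

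The stake is the description of safety by lirilumab dose. The primary objective of Part 1 is safety and tolerability, and its dose levels may hold as few as 3 subjects. An event counted under the assigned dose, when another dose was given throughout, is attributed to a dose the subject never had. Parts 1 and 2 are not randomized, so as-assigned grouping protects no randomized comparison in these tables.

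**Working it through.** The plan states no figure on this point, so there is none to reproduce. The check is a comparison of the text, followed by simple proportions.

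**Step 1: where each type of subject is counted**

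| Subject | Exposure tables (7.4, as treated) | Safety tables (7.6, as assigned) |
|---|---|---|
| Correct treatment throughout | assigned group | assigned group |
| Wrong treatment for part of the period | assigned group (default in 6.2) | assigned group |
| Wrong treatment for the entire period | received group (exception in 6.2) | assigned group |

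Only the last row differs.

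**Step 2: what differs for that subject**

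In the safety tables the assigned group has one more subject than in the exposure tables, and the received group has one fewer. Discontinuations by reason (SAP 7.4.2) and adverse events leading to discontinuation (SAP 7.6.4) would also fall in different columns for the same subject.

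**Step 3: the exposure-adjusted rates**

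SAP 7.6.7 lies inside Section 7.6 and computes its own patient-years from first dose, last dose and follow-up. It does not use the 7.4 tables. Events and patient-years therefore share the as-assigned basis. Where those rates are shown by treatment, they would sit under a dose not received, but numerator and denominator agree.

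**Step 4: size in a single dose level**

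Inputs: 3 to 15 subjects per dose level (SAP Table 2.1.1.1-1). Assumption, not in the documents: one subject on the wrong treatment throughout, with an event that nobody else in either group had. Sizes are counted by assignment.

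| Group | n | As assigned | As treated | Shift |
|---|---|---|---|---|
| Assigned level | 3 | 1/3 = 33.3% | 0/2 = 0% | 33.3 points |
| Assigned level | 15 | 1/15 = 6.7% | 0/14 = 0% | 6.7 points |
| Received level | 3 | 0/3 = 0% | 1/4 = 25.0% | 25.0 points |
| Received level | 15 | 0/15 = 0% | 1/16 = 6.3% | 6.3 points |

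**Step 5: size in a pooled Dose Level 4 group**

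Inputs: escalation 3 to 15, Part 1 expansion about 97 to 124 (SAP Table 2.1.1.2-1), and Part 2 about 35 at Dose Level 4 (SAP 2.1.2). Assumption: the expansion cohorts were also treated at Dose Level 4.

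- Smallest: 3 + 97 + 35 = 135, and 1/135 = 0.7%.
- Largest: 15 + 124 + 35 = 174, and 1/174 = 0.6%.

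SAP 5.2 allows some escalation subjects to count toward the tumor cohorts, so these sums may count a few people twice. Without the escalation subjects the smallest total is 97 + 35 = 132, and 1/132 = 0.8%, still under 1 point.

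**The case against.** The strongest case on the other side has four parts.

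**It may never arise.** Parts 1 and 2 are open-label, escalation subjects were assigned to dose levels in sequence, and no document reports a subject on the wrong treatment throughout. This stands, and is why the severity is the lowest.

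**Any such subject can be traced.** The deviation listing names the case, drug administration is listed by patient and visit (SAP 7.4.1), and all adverse events are listed. A reader could reassign the events by hand. This also stands, but the summary tables would remain misattributed, and most readers use those.

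**The as-assigned wording was chosen.** The SAP's document history records a change from as treated to as assigned in an early version. That shows intent somewhere in the document. It gives no reason, and the current text still defines as treated in 6.2 and uses it in 7.4. If as assigned was meant throughout, 7.4 needs correcting; otherwise 7.6 does.

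**The consequences are narrow.** A reader might infer more than the documents support:

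- *That any dosing error is misattributed.* Under SAP 6.2, a subject wrongly dosed for part of treatment stays in the assigned group on both bases, and the fix does not change that.
- *That the exposure-adjusted rates mix two bases.* SAP 7.6.7 computes its own patient-years within the safety section.
- *That the randomized comparison is affected.* Part 3 is listed only.
- *That dose escalation was affected.* Escalation was decided on Cycle 1 dose-limiting toxicities under their own evaluability rules (SAP 2.1.1.1), and Part 1 is complete.

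**Conclusion.** The inconsistency is in the current SAP and nothing in either document reconciles it. As written, a Part 1 or Part 2 subject on the wrong treatment for the entire period is counted under the received dose for exposure and the assigned dose for safety.

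The effect is zero if there is no such subject. With one, who had the event in question, the shift in the assigned level is about 7 to 33 points for 15 down to 3 subjects. The upper figure needs a level left at its minimum size. In a pooled Dose Level 4 group it is under 1 point; this assumes the expansion cohorts were treated there. Protocol 1.4.13.3 makes that plausible, because it says most of the 159 subjects treated by 30-Aug-2016 were at that level, but it does not give the dose cohort by cohort. The point therefore matters mainly for the small lower dose levels. It is a free improvement, not a threat to the study's conclusions.

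**What to change.** In SAP 7.6, replace as assigned with as treated as defined in SAP 6.2, so that safety and exposure share one basis. Footnote in both sets of tables any subject whose assigned and received groups differ.

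If the sponsor prefers to keep as assigned for safety, use it in SAP 7.4 as well, state the reason, and keep the footnote. As treated is the better choice here because these are non-randomized dose-group summaries, and events should be attributed to the dose received.

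The cost is one changed phrase and a footnote. No new data are needed, and no result changes unless a subject was on the wrong treatment throughout.

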4 ENDPOINTS

4.1 Primary Endpoints

Safety and preliminary anti-tumor activity are the primary objective for all parts (i.e. Parts 1, 2, 3, and 5) except Part 1, where the primary objective is to assess the safety and tolerability of lirilumab given in combination with nivolumab, and Part 3, where the primary objective is to assess estimate the objective response rate of lirilumab given in combination with nivolumab.

For safety objective, all subjects who receive at least 1 dose of study drug will be evaluated for safety as measured by the incidence of AEs, SAEs, AEs leading to discontinuation, and deaths assessed during treatment and for 150 days in follow-up. In addition, clinical laboratory test abnormalities will be examined.

All non-serious AEs will be collected from Day 1 until 150 days after the subject's last dose of study drug or until they discontinue the study as per study protocol Section 3.5 and all SAEs must be collected from the date of the subject's written consent until 150 days after discontinuation of dosing or until they discontinue the study as per study protocol Section 3.5. AEs will be categorized

using the most current version of MedDRA. AEs and laboratory values will be graded according to the National Cancer Institute (NCI) Common Terminology Criteria for Adverse Events (CTCAE) version 4.03.

For preliminary-antitumor activity, the primary endpoint will be to estimate ORR by derived BORs per RECIST v1.1 using investigator-provided tumor assessments for all Parts. The BORs for investigator-assessed responses per RECIST v1.1 for Parts 3 and 5 will be listed. Details regarding the definition of ORR will be given in the upcoming Secondary endpoint section for preliminary antitumor activity.

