7.1 General Methods

Continuous variables will be summarized using descriptive statistics, i.e., medians, minimums, maximums, and means with standard deviations/(or standard errors of the mean). Categorical

variables will be summarized by frequencies and percentages. Percentages will be rounded and may not always add up to 100. Confidence intervals for binomial proportions will be derived using the Clopper-Pearson method.²³

Unless otherwise specified, the following general rules will be applied:

- Data from Part 1 and Part 2 will be combined, with safety and tolerability data summarized by treatment group, and efficacy data summarized by tumor types.
- All results from Part 3 and Part 5 will be included in listing only.
- Additional outputs may be provided for SCCHN participants as appropriate.

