7.6.7 Multiple Events

Analyses that take into account the multiple occurrences of a given adverse event will be conducted. In order to prepare these analyses, the CRF data will be processed according to standard BMS algorithms²⁶ in order to collapse adverse event records into unique records based on the preferred term. This data will be presented as the rate per 100 patient-years of exposure (observation period). This analysis will take into account all on-treatment events (allowing more than 1 event per subject) and the total duration of exposure. The patient-years exposure will be computed as the sum over the subjects' exposure expressed in years where the duration of exposure is defined as

- Date of last dose of study treatment date of first dose of study treatment + 100+1 days, for subject who are off study treatment and were followed at least 100 days after last dose of study medication. For patients being followed for 150 days, please use 150 days in above calculation.
- Last known date alive- date of first dose of study medication +1, for subjects who are still ontreatment or who are off study treatment and were followed less than 100 days after last dose of study medication.

When specified, the 95% CI of the rate per 100 patient years of exposure will be derived using normal approximation and variance estimation proposed in Cook and Lawless²⁷ (optional). Summary tables will be generated for part 1 and 2 combined.

Summary:

The following summary tables will be provided:

- Summary of frequency of unique adverse events
- Total number and rate (exposure adjusted) of occurrences for all AEs occurring in at least 5% of the subjects treated across treatments.

Listing:

Unique instances of all AEs, i.e., after duplicates have been eliminated and overlapping and contiguous occurrences of the same event (i.e., same PT) have been collapsed.

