7.6.8 Clinical Laboratory Evaluations

The results of all protocol-specified clinical laboratory tests, as well as laboratory results outside of the normal range, will be listed. Scheduled laboratory measurements and corresponding change from baseline values will be summarized by treatment and nominal visit for each laboratory test.

The analysis will be based on All Treated Subjects with available laboratory test result ontreatment and up to and including 100 (or 150) days of the last dose of study medication. Laboratory results will be categorized according to NCI CTCAE (version 4) grade.

Summary tables will be generated for Part 1 and 2 combined. Listings will include all available data from Parts 1, 2, 3, and 5.

Summary:

The number (%) of subjects with the following will be summarized by treatment and overall, if appropriate, using the worst CTC grade on-treatment per subject.

- Post-baseline grade
- Grade change from baseline
- Descriptive statistics of laboratory test result and their changes from baseline by treatment and study day

Listing:

A by-subject listing of these laboratory parameters will be provided.

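### SAP 7.1 and 7.6 give Parts 3 and 5 no safety summary tables, although safety is a primary endpoint in Part 5 and Part 3 is the only randomised comparison

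*SAP*

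**What the plan says.** SAP 7.1 opens its general rules with "Unless otherwise specified, the following general rules will be applied" and then states "All results from Part 3 and Part 5 will be included in listing only". Parts 1 and 2 are pooled and summarised. The only other outlet in that section is optional: "Additional outputs may be provided for SCCHN participants as appropriate".

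SAP 7.6 first says "All AEs will be summarized and listed by SOCs and PTs", with no part excluded. Its last paragraph narrows this: "Summary tables will be generated for Part 1 and 2 combined. Listings will include all available data from Parts 1, 2, 3, and 5". The limit returns in 7.6.7 ("Summary tables will be generated for part 1 and 2 combined") and in 7.6.8 ("Summary tables will be generated for Part 1 and 2 combined").

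SAP 4.1 defines the safety endpoint differently: "all subjects who receive at least 1 dose of study drug will be evaluated for safety as measured by the incidence of AEs, SAEs", together with discontinuations due to AEs and deaths. It exempts no part.

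Protocol 8.4.3 requires AEs to be both listed and tabulated by system organ class (SOC), preferred term (PT) and treatment, and laboratory and vital sign data to be summarised by treatment. It also provides for safety summary tables by treatment arm, qualified by 'if applicable'. Protocol 8.3.1.4 makes safety one of two primary endpoints in Part 5, and 8.3.2.2 makes it a secondary endpoint in Part 3.

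**The concern.** A listing shows individual records; it does not report an incidence. If the SAP is followed, readers of the study report must count Part 5 rates themselves, although safety is a primary endpoint there and the triplet is being tested for the first time (protocol 1.5). The only safety conclusion on the triplet in the documents is a preliminary look at 10 lead-in subjects. The SAP text commits to no final rate to set beside it.

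For Part 3 the loss is the comparison. Arm A against Arm B is the only place in this trial where toxicity added by lirilumab can be separated from that of nivolumab by randomisation. The pooled Part 1 and 2 tables have no nivolumab-alone arm.

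**Working it through.** The plan gives no figure to reproduce here. The check is a comparison of texts, a count of outputs, and an illustration of precision.

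**1. Commitments side by side**

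| Source | Part 3 | Part 5 |
|---|---|---|
| SAP 4.1 | Incidence in all dosed subjects | Same |
| SAP 7.6, second paragraph | AEs summarised and listed | Same |
| Protocol 8.4.3 | AEs listed and tabulated by treatment | Same |
| SAP 7.1 | Listing only | Listing only |
| SAP 7.6, last paragraph | Listing only | Listing only |
| SAP 7.6.7 | No summary table | No summary table |
| SAP 7.6.8 | Listing only | Listing only |

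The first three rows cannot be met if the last four are followed.

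**2. Is anything otherwise specified?** No subsection from 7.6.1 to 7.6.8 names a Part 3 or Part 5 summary table. Two subsections do not repeat the limit: 7.6.5 (hypersensitivity and infusion reactions by anti-drug antibody status) and 7.6.6 (immune-mediated AEs, with one table for SCCHN participants). Neither names Part 3 or Part 5, so both fall under the scope statement of 7.6. SAP 7.4.1 points the same way: it assigns ipilimumab duration of therapy to a Part 5 listing.

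**3. Was the protocol commitment withdrawn?** Revised Protocol 12 marks what it dropped, such as outcomes research (8.4.7), survival follow-up (3.7) and most PK and anti-drug antibody sample analysis (5.7.3.3). It left 8.4.3 unchanged. AE collection continues to 150 days after the last treatment or until subsequent anti-cancer therapy (5.3). The SAP document history for versions 2.0 and 2.1 records no decision to drop Part 3 or Part 5 safety tables.

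**4. Outputs affected**

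- 7.6.1, AEs, any and related: 2
- 7.6.2, deaths: 1
- 7.6.3, SAEs, any and related: 2
- 7.6.4, AEs leading to discontinuation, any and related: 2

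2 + 1 + 2 + 2 = 7 per part, and 7 × 2 = 14 for both parts.

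**5. What such tables could show.** Final numbers treated are not stated. Part 5 had 10 lead-in subjects treated as of 06-Apr-2018, with about 40 planned. Part 3 planned 150 + 75. Smaller sizes are assumed to show a range; for Part 3 these are a third of plan, 150/3 = 50 and 75/3 = 25. With zero events, the upper limit of the exact (Clopper-Pearson) two-sided 95% interval is 1 − 0.025^(1/n).

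| Setting | n | Upper limit |
|---|---|---|
| Part 5, lead-in | 10 | 30.8% |
| Part 5, assumed | 20 | 16.8% |
| Part 5, planned | 40 | 8.8% |
| Part 3 Arm A, planned | 150 | 2.4% |
| Part 3 Arm A, one third | 50 | 7.1% |
| Part 3 Arm B, planned | 75 | 4.8% |
| Part 3 Arm B, one third | 25 | 13.7% |

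For an event seen in 30% of Part 5 subjects, the exact 95% interval is 7% to 65% at 3/10 and 17% to 47% at 12/40.

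**The case against.** The best defence is that this is deliberate abbreviated reporting. Parts 3 and 5 closed early for lack of a differential efficacy signal, SAP section 1 records the closure, and the limit is repeated too often to be a slip. Within 7.6, the specific scope statement can be read as overriding the general sentence. The by-arm sentence in protocol 8.4.3 is qualified. The listings lose no data, and if Part 5 stopped near 10 subjects, counting from them is easy. SAP 9 places the complete list of report outputs in a Data Presentation Plan, which may already contain the tables.

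Some of this stands. The impact is uncertain, the precision figures depend on assumed sizes, and few subjects may have been treated. The rest does not answer the point:

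- Neither document gives closure as a reason to depart from 8.4.3.
- The AE tabulation sentence in 8.4.3 carries no qualifier.
- SAP 4.1 still defines the endpoint as incidence.
- If the Data Presentation Plan does contain the tables, it contradicts SAP 7.1 and 7.6, and the SAP still needs correcting.

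**Conclusion.** The concern holds. The SAP text commits to none of its seven AE, SAE, discontinuation and death summaries for Part 5 or for Part 3, contrary to SAP 4.1 and to the unqualified AE tabulation sentence in protocol 8.4.3. The sponsor should correct this. It matters most for Part 5, where safety is primary; in Part 3 safety is secondary, but the comparison is randomised.

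Confidence in the reading of the text is high. The effect on the final report is less certain, because it depends on final enrolment and on the Data Presentation Plan, neither of which is available. No sample size, power or alpha figure is affected.

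**What to change.** 1. **SAP 7.1, listing-only rule for Parts 3 and 5:** insert the exception 'except safety'.
2. **SAP 7.6, last paragraph:** keep the pooled Part 1 and 2 statement and add: *For Part 5, and for Part 3 by arm (All Treated), the SOC/PT worst-grade tables in 7.6.1, 7.6.3 and 7.6.4 and the deaths summary in 7.6.2 will also be generated.*
3. **Laboratory results and vital signs:** protocol 8.4.3 also calls for these by treatment. Either extend the 7.6.8 and 7.6.8.2 summaries to both parts, or record in the SAP that they stay in listings and why.

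An overview table of n/N (%) is optional. Recording a reason for keeping all safety data in listings would reconcile the documents but would not deliver the incidence defined in SAP 4.1, so it is not the preferred route. The edit to 7.1 concerns safety only; it leaves the listing-only treatment of Part 3 response rate as it is.

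The cost is two wording changes and 14 outputs built from existing table specifications, plus any laboratory and vital sign tables. No new data are needed. The downside is a little extra programming and imprecise rates if few subjects were treated.
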